Getting pregnant using IUI can cost \$250-500 per insemination before accounting for the cost of the testing and other imaging done as part of the process. IVF is even more expensive and invasive. According to Katz et al. 2011, the median per-person cost of IVF was approximately \$24,373 (for just IVF) to \$38,015 (for IVF-donor egg). Voorhis et al. 1997 found ICI to cost \$7.800-10,300 while Assisted Reproductive Therapy (ART) cost \$37,00 - 76,000. The cost difference between IVI/ICI, IUI and ART therapies such as IVF is significant. This makes cost a consideration for people attempting to conceive.

The good news is a number of studies such as Cohlen and Ombelet 2014 and Banerjee and Singla 2017, demonstrate the viability of using IVI/ICI as a means of AIH. The benefits of ICI is that it can be done in the privacy of the home, is relatively low cost, and over a 6 cycle time frame seems to have comparable rates to its more expensive counterparts.

Cohlen and Ombelet 2014 showed that for many couples with cervical factor infertility, psychological sexual dysfunction, physiological dysfunction, unexplained infertility and mild to moderate male subfertility using artificial insemination with a husband's sperm (AIH) was a

preferred treatment option. Banerjee and Singla (2017), tested couples with unconsummated marriages due to vaginismus, erectile dysfunction and premature ejaculation. They found 69% of couples ages 20-32, 43% ages 33-36, and 25% over 36 years old conceived using IVI. This is comparable to the expected 10-35% pregnancy rate of IUI.

Additionally, Kop et al. 2018 conducted a literature review to determine if there was a difference between pregnancy rates and live births of IUI versus ICI. They reported that out of six trials totalling 708 women. They concluded that there was not enough evidence to determine that IUI resulted in more live births or pregnancies than ICI.

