4 STUDY DESIGN

4.1 Overall Design

This is a post-market retrospective cross-sectional observational study of people using the Mosie Kit for at-home insemination. The goal of the study is to understand the pregnancy rate resulting from using the Mosie Kit of people with known fertility issues or those wishing to conceive without intercourse due to medical reasons such as vaginismus or being in a LGBTQ relationship desiring a child.

This study uses a convenience sample of people who purchased the Mosie Kit in the past 8 complete months prior to the commencement of the study. The complete known list of people will be invited to participate in the study. For the primary hypothesis 1, all study participants will be treated as one group initially. Subsequently, the study participants may be divided into groups according to their age, the type of relationships (heterosexual or LGBTQ), and/or source of infertility to examine the hypothesis as it relates to these subgroups if sufficient sample size indicates this is appropriate; this analysis corresponds to the tertiary hypothesis.

Primary hypothesis 1: Pregnancy rates using the at-home insemination Mosie Kit to deposit semen near or at the cervix (i.e. intracervical insemination) are equivalent or better than traditional in doctor's office intrauterine insemination.

Given the participants can either be people with fertility issues or people in LGBTQ relationships without known problems conceiving or single women wishing to conceive, another primary hypothesis that will be examined is the difference of pregnancy rates in each of these groups. Specifically, the primary hypothesis related to this is as follows:

Primary Hypothesis 2: Pregnancy rates of LGBTQ people or single women using the Mosie Kit where the female has no know fertility issues will be higher than that of heterosexual people with a known fertility cause or those that are designated as having an unexplained fertility issue.

The secondary hypothesis will examine the use of the Mose Kit and its safety as perceived and reported by the study participants. For these hypotheses the participants will be examined as one group as well as categorized by age group and type of relationship. Specifically, the secondary hypothesis will be as follows:

Secondary Hypothesis 1: The participants perceived the Mosie Kit to be easy to use for its intended purpose.

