This study does not use randomization. While no control group will be examined for the study, determining the result of some of the hypotheses is based on using the reported pregnancy rate of IUI in the literature. Specifically, the reported rate of pregnancy with IUI is as high as 20% in one cycle according to the American Pregnancy Association. According to the CDC, it can range between 10-35% across 6 cycles.

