4.2 Scientific Rationale for Study Design

The retrospective cross-sectional study design was selected because the desire is to examine the pregnancy rates and perception of useability and safety of the Mosie Kit. Since this is a post-market study, the use of an existing group of participants who voluntarily purchased and used the Mosie Kit exists and provides an excellent group of participants to study. The past experiences of these participants will provide valuable information for future participants on the success rate of at-home insemination, information as to the ease of use of the instructions included in the kit, ease of use of the kit, and perceived safety.

The rationale for examining the participants first as a complete cohort and then stratified by type of relationship, infertility source, and age group is that the primary hypotheses relate to overall pregnancy rates using the at-home insemination Mosie Kit and the rate of pregnancy in women without a known fertility cause wanting to get pregnant without intercorse. The type of relationship is also important because a woman in an LGBTQ relationship without fertility issues is more likely to easily get pregnant than a heterosexual female with fertility issues once the semen is deposited at or near the cervix. While there might be LGBTQ women that also have a known cause of fertility, they will be examined by type or relationship as well as by infertility source. Likewise, single women will be categorized by their known infertility source or as not having a known fertility issue. It is important to study the difference between the two groups and explore the impact on the overall pregnancy rate of Mosie Kit users.

Additional hypotheses aim to examine more specifics related to each stratification. For example, age is known to affect fertility rates. Women ages 20-30 are more likely to get pregnant than those in their 40s. The source of infertility may also indicate underlying biological or physical issues that might mediate the pregnancy rates causing different rates of success in each of the groups. All the information obtained through this study will be used to benefit people who are trying to get pregnant and are experiencing infertility issues. Specifically, the study will examine the viability and success rate of at-home insemination.

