9.1 Statistical Hypotheses and General Statistical Approach

The primary objective is to understand the outcome of using the Mosie kit for Intracervical insemination, i.e. pregnancy rate after its use. Specifically the hypothesis is as follows.

Primary hypothesis 1: Pregnancy rates using the at-home insemination Mosie Kit to deposit semen near or at the cervix (i.e. intracervical insemination) are equivalent or better than traditional in doctor's office intrauterine insemination (IUI). Conversely the null hypothesis is that the pregnancy rates using the at-home insemination Mosie Kit to deposit semen near or at the cervix do not have higher rates of pregnancy than in doctor's office IUI.

Analysis: Comparison of total rates of pregnancy using the Mosie Kit to the 10-20% rate reported for IUI by the American Pregnancy Association.

Primary Hypothesis 2: Pregnancy rates of LGBTQ couples or single women using the Mosie Kit where the female has no know fertility issues will be higher than that of heterosexual couples with a known fertility cause or those that are designated as having an unexplained fertility issue. The alternative hypothesis is that people with no known

fertility issues using the Mosie Kit will have less pregnancies than heterosexual couples with known fertility issues.

Analysis: Rate of pregnancy using the Mosie Kit will be obtained for the following groups: LGBTQ couples where carrying female has no known fertility issues, LGBTQ couples where carrying female has a known fertility issue, Heterosexual people with no known fertility issue, Heterosexual people with a known fertility issue, Single females with no known fertility issue and Single females with a known fertility issue. The rates of each group will be analyzed using descriptive statistics and the aggregate of the 3 groups with fertility issues will be compared with the aggregate of the 3 groups without fertility issues. An ANOVA will be used to compare the differences between groups.

Secondary Hypothesis 1: The participants perceived the Mosie Kit to be easy to use for its intended purpose. The alternative hypothesis is that the participants perceive the Mosie Kit to be difficult to use for its intended purpose.

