9.4.2 Sub-Group Analyses

All endpoints (primary, secondary and tertiary) will be analyzed based on age, sex, race.ethnicity, SES, relationship preference, male/femaile infertility issues. Only aggregate

information will be used in the final analysis. No tabulation of individual participant data will be used in reporting findings.

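### Section 4.1 lets the kit-versus-IUI hypothesis be re-examined by age, relationship type and infertility source, but no IUI rate is given for any of these subgroups

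*Combined protocol and SAP*

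**What the plan says.** Primary Hypothesis 1 is that kit pregnancy rates "are equivalent or better than traditional in doctor's office intrauterine insemination" (section 4.1). All participants are first treated as one group. They may then be divided by age, relationship type and/or infertility source "to examine the hypothesis as it relates to these subgroups if sufficient sample size indicates this is appropriate". Section 4.1 adds that "this analysis corresponds to the tertiary hypothesis".

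The analysis line for this hypothesis in section 9.1 is "Comparison of total rates of pregnancy using the Mosie Kit to the 10-20% rate reported for IUI by the American Pregnancy Association". Section 4.1 explains that there is no control group and that literature IUI rates stand in for one. It says "the reported rate of pregnancy with IUI is as high as 20% in one cycle" and also cites 10-35% across 6 cycles. None of these figures is broken down by age, relationship type or infertility source, and no standardisation is planned.

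The protocol also says that pregnancy rates differ across these factors. Section 4.2 states that "age is known to affect fertility rates". Section 2.2 reports, for home intravaginal insemination (IVI) in unconsummated marriages: "They found 69% of couples ages 20-32, 43% ages 33-36, and 25% over 36 years old conceived using IVI". The section 3 table expects higher rates in people without known fertility issues.

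Section 9.4.2 says: "All endpoints (primary, secondary and tertiary) will be analyzed based on age, sex, race.ethnicity, SES, relationship preference".

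**The concern.** Read literally, the hypothesis to be re-examined in subgroups is the comparison with IUI. If a subgroup's kit rate is set against an undivided IUI figure, the difference has two parts: any effect of the kit relative to IUI, and the gap between that subgroup's fertility and the fertility of whatever population lies behind the IUI figure. The plan has no means of separating them. The same applies to relationship type and infertility source, because users without a known fertility problem are expected to conceive more often by any method.

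The pooled verdict is a separate matter. The problem arises even if the pooled comparison is exactly right. A larger subgroup does not help, because this is bias and not imprecision.

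Section 2.3.2 says the results should help users decide whether the kit suits them, including by comparison with IUI, and section 10.1.3 allows aggregate results to be used in marketing. A subgroup statement about IUI that reflects only age or diagnosis would mislead those readers.

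**Working it through.** **The plan's own figure.** Section 9.2 gives a 95% half-width of 4.4 points at 500 surveys and 5 points at 384. With p = 0.5, 1.96 × √(0.25/500) = 4.38 points and 1.96 × √(0.25/384) = 5.00 points, so both reproduce. They describe the whole sample. No subgroup size, margin or power is stated.

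**Inputs from the documents.** N = 500 (section 9.2); significance level 0.05, one-tailed for directional hypotheses (section 9.4.1); IUI comparators 10-20% (section 9.1) and up to 35% (section 4.1); age gradient 69:43:25 (section 2.2).

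**Assumptions.** Kit and IUI have identical rates at every age. IUI follows the 69:43:25 gradient, although it is quoted for IVI. The 500 respondents split 200/150/150 by age band. The true overall rate is 20% or 15%.

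**Rates under equality.** The weighted mean of the gradient is 0.4 × 69 + 0.3 × 43 + 0.3 × 25 = 48.0%.
- Overall 20%: scale 0.20/0.48 = 0.4167, giving 28.7%, 17.9% and 10.4%. The gaps from 20% are +8.7, -2.1 and -9.6 points.
- Overall 15%: scale 0.15/0.48 = 0.3125, giving 21.6%, 13.4% and 7.8%. The gaps from 15% are +6.6, -1.6 and -7.2 points.

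The kit effect is zero in every band, so these gaps are entirely age.

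**Probability of a false 'better than IUI' in the youngest 200** (exact binomial, one-sided 5%):

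| Benchmark | Pregnancies needed of 200 | Overall 20% | Overall 15% |
|---|---|---|---|
| Point equal to the overall rate | 50 (at 20%); 39 (at 15%) | 90% | 79% |
| 20% end of the section 9.1 range | 50 | 90% | 14% |
| 35%, upper six-cycle figure | 82 | about 0.01% | below 0.01% |

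**Sensitivity to the assumptions** (benchmark equal to the overall rate):
- Half the gradient on the log scale, overall 20%: 46%.
- Age mix 50/30/20: 73% at 20% and 61% at 15%. Age mix 60/25/15: 58% and 50%.
- A gap of only 5 points with 150 users: 42% at 20% and 45% at 15%. A gap of 3 points: about 22%.

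**Sensitivity to the rule.** If 'better' requires the whole 95% interval to lie above the 10-20% range, a subgroup of 200 with a true rate of 22% is falsely called better about 10% of the time. If it requires only the point estimate to exceed 20%, the figure is 72%.

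**With a matched comparator.** With equal thirds (167 per band), testing the youngest band against its own IUI rate gives a false 'better' of 4.7% at an overall 20% and 3.8% at 15%, so the nominal level is restored.

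**The case against.** The strongest reply is that the plan does not actually call for a subgroup test against IUI. Section 9.1 compares only total rates with IUI, and section 9.4.1 refers back to section 9.1 for the analysis of each hypothesis. The section 4.1 wording is permissive and depends on sample size. Its link to the tertiary hypotheses suggests comparisons among kit users. Section 9.4.2 speaks of endpoints: analysing pregnancy rate by age is not the same as testing each age band against IUI.

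Most of this stands, and it limits the point to what section 4.1 permits. It does not remove that permission. The hypothesis named there is the IUI one, and the tertiary hypotheses include no age hypothesis and supply no IUI rate.

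A reader might go further and infer that the plan will declare the kit better than IUI in the young and worse in the old, with probability above 90%. The documents do not support that:
- No decision rule is stated for Primary Hypothesis 1, and the comparator is a range. The high figures come from replacing the range with a single point.
- 'Worse than IUI' is not a planned verdict. The section 9.1 null is that kit rates are not higher, and failing to reject it is not a finding of inferiority. A lower-tail test of the oldest 150 against 20% would give 94% at an overall 20%, but against the 10% end of the range it gives 2%.
- Calling the IUI figures all-comers rates is an inference. The documents do not describe the populations behind them.

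Section 2.2 does cite an IUI rate of 15% in single fertile women, but as background and not as a comparator. The caution about generalisability in section 5.5 does not address the mismatch.

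**Conclusion.** The point holds as a gap in what the plan permits. Section 4.1 allows the IUI hypothesis to be carried into subgroups, no IUI figure is matched to those subgroups, and the protocol's own statements on age and fertility status imply that such comparisons would be confounded. The direction is clear: an undivided benchmark tends to favour the kit in younger users or those without fertility problems, and to disfavour it in older users.

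The size is not settled by the documents. With the quoted gradient and a 200/150/150 split, the chance of a false 'better' in the youngest group runs from about 90% to 0.01% or less, depending on which IUI figure is the benchmark and what the true overall rate is. It also falls with a milder gradient or a younger sample. The upper figures show what one natural reading would allow. They do not forecast what the analysis will conclude.

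**What to change.** In sections 4.1 and 9.1, state that the comparison with IUI applies to the total sample only, unless an IUI rate for the same subgroup is pre-specified with its source. Otherwise, report subgroup kit rates with 95% confidence intervals, compare subgroups only with each other, and make no subgroup statement of equivalence to, or superiority over, IUI.

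This takes about one sentence in each section and needs no new data. The small downside is that the sponsor gives up subgroup claims against IUI that lack a matched comparator.

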Since [name] sperm freezing success in 1953 with a subsequent live birth, collecting and using sperm for insemination in humans was made possible. However, it would be more than a decade before it became legally possible as it was initially ruled as contrary to public policy and good morals. In the 1960s and 70s, sperm selection and washing techniques led to Intrauterine insemination (IUI) which placed the sperm even further into the woman's body by putting it directly into the uterus. By the 1970s sperm banks in the US became popular. Also in the 1970s, Steptoe and Edwards introduced the world to In-Vitro Fertilization (IVF). More recently, techniques such as intratubal insemination, and intraperitoneal insemination have been added to the available conception methods. During the last decades the popularity of Intrauterine Insemination (IUI) increased because it was safer, painless, and more cost-effective. Additionally, more information has become available about sperm selection techniques and now there is a greater understanding of many of the causes of infertility.

The most popular method of insemination is to use the husband's sperm (Artificial Insemination by Homologous or Husband (AIH)). In some cases anonymous donor sperm is used. Intracervical (ICI) or intravaginal insemination (IVI) are terms used interchangeably to describe the insemination technique colloquially known as the "turkey baster method". This method consists of placing the semen into the vagina at or near the cervix. In the United States, IUI is the most frequently doctor assisted technique. Some researchers have examined the success rates of each technique. ICI/IVI has been found to have a per cycle pregnancy rate of 10-15% while IUI has been found to be slightly higher up to 10-35%. Meanwhile techniques such as IVF can be as high as 31% in people under 35 years of age and as low as 3% for those above 43 according to the CDC.

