Carroll and Palmer (2001) conducted a prospective randomized cross over control study on 62 single fertile women choosing to use donor sperm. They had a total of 189 cycles (94 IUI and 95 ICI). The resulting pregnancy rate was 15% and 9% respectively (p=0.04) which indicated that IUI was more effective than ICI. On the other hand, Hogerzeil et al. (1988) studied 53 women who either had at home ICI (n=29) or in clinic ICI (n=24). In the first 6 cycles 13 pregnancies resulted in the home ICI group while only 11 pregnancies resulted in the clinic group. Additionally, they followed 138 couples who did not meet the inclusion criteria. Of these 45 had opted for at home insemination and 20 of them ended up with a pregnancy.

In conclusion, there is a lot of room to learn more about the pregnancy rates of ICI and the experience of at-home artificial insemination. With 12% of women of child bearing age experiencing infertility there is an important contribution to be made to the fertility field. Using the Mosie Baby at-home artificial insemination kit is a low cost option that could potentially be a first line alternative for many people seeking to conceive. Therefore, it is important to understand the experience and pregnancy rates of people who have chosen to use the Mosie Kit to get pregnant at home. This study will provide valuable information for the fertility industry as a whole, as well as, will provide information for a follow up study where people choosing to use the Mosie Kit will be prospectively followed to capture their data in real time. Together these studies will provide a better understanding of at-home insemination success, safety and perception.

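### The 10-35% IUI rate is labelled six-cycle in section 4.1 but sits in a per-cycle sentence in section 2.2, and as a six-cycle figure it conflicts with the plan's other rates

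*Combined protocol and SAP*

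**What the plan says.** The study has no control group. Section 4.1 (Overall Design) says that some hypotheses are decided using IUI pregnancy rates from the literature, and gives two:

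- a one-cycle rate attributed to the American Pregnancy Association: "the reported rate of pregnancy with IUI is as high as 20% in one cycle";
- a six-cycle rate attributed to the CDC: "According to the CDC, it can range between 10-35% across 6 cycles".

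The second is the only IUI figure in the document labelled as six-cycle.

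Section 2.2 (Background) uses the same range twice more. One sentence opens with a per-cycle unit: "ICI/IVI has been found to have a per cycle pregnancy rate of 10-15% while IUI has been found to be slightly higher up to 10-35" percent. Later, after reporting that 69%, 43% and 25% of couples in three age bands conceived with IVI, it says: "This is comparable to the expected 10-35% pregnancy rate of IUI". No time unit is given there.

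Section 2.2 also reports two insemination studies. A randomised crossover in 62 single fertile women covered 94 IUI and 95 ICI cycles: "The resulting pregnancy rate was 15% and 9% respectively (p=0.04) which indicated that IUI was more effective than ICI". A randomised study of ICI at home (29 women) or in clinic (24 women) reported: "In the first 6 cycles 13 pregnancies resulted in the home ICI group while only 11 pregnancies resulted in the clinic group".

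The primary endpoint (section 3) is pregnancy after up to 6 cycles. The section 9.1 analysis of primary hypothesis 1 compares the kit's total pregnancy rate with 10-20% for IUI and states no time unit.

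**The concern.** One range carries two time units. If 10-35% is per cycle, the six-cycle label in 4.1 is wrong. If it is six-cycle, the sentence in 2.2 sets a per-cycle ICI rate beside a cumulative IUI rate and calls the second slightly higher.

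This matters because the endpoint runs over up to six cycles, while the 10-20% in section 9.1 appears to be a one-cycle rate: section 4.1 ties its upper end, from the same association, to one cycle. Anyone who notices that mismatch will look for a six-cycle IUI figure, and the plan offers only this one. If it is a mislabelled per-cycle rate, switching to it would not repair the comparison. Primary hypothesis 1, that the kit is equivalent to or better than IUI, would still be judged against too low a bar.

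**Working it through.** **Inputs.** IUI 10-35% labelled six-cycle, and IUI up to 20% in one cycle (4.1). ICI 10-15% per cycle; IUI 15% of 94 cycles and ICI 9% of 95 cycles; six-cycle ICI counts 13/29 and 11/24 (all 2.2). The 15% and 9% are read as per-cycle because the denominators given are cycles.

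**Step 1: can 10-35% be reproduced as a six-cycle rate?** With a constant per-cycle rate p and six completed cycles, the cumulative rate is 1 − (1 − p)^6.

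| Per-cycle rate | Over six cycles |
|---|---|
| 9% | 43.2% |
| 10% | 46.9% |
| 15% | 62.3% |
| 20% | 73.8% |
| 35% | 92.5% |

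None of the plan's per-cycle rates gives a six-cycle figure within 10-35%.

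**Step 2: the inverse.** The implied per-cycle rate is 1 − (1 − c)^(1/6).

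- c = 10%: 1 − 0.90^(1/6) = 1.7%
- c = 35%: 1 − 0.65^(1/6) = 6.9%

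Both lie below the lowest per-cycle rate quoted for either method (ICI 9%).

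**Step 3: the plan's six-cycle ICI counts**, with exact 95% intervals.

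- Home: 13/29 = 44.8% (26.4-64.3)
- Clinic: 11/24 = 45.8% (25.6-67.2)
- Pooled: 24/53 = 45.3% (31.6-59.6); one-sided exact p against 35% = 0.079

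Both point estimates exceed 35%, but every interval includes it. The further 20/45 home users in section 2.2 are left out because no cycle limit is stated for them.

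**Step 4: relaxing the constant rate.** Suppose fecundability varies between couples as a beta distribution with mean m and a + b = s, where a = ms. The six-cycle rate is then 1 − Π(b + k)/(a + b + k) for k = 0 to 5. The values of s are assumptions.

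| Mean per cycle | s = 2 | s = 5 | s = 10 |
|---|---|---|---|
| 10% | 28.1% | 35.6% | 40.0% |
| 15% | 39.5% | 49.0% | 54.3% |
| 20% | 49.5% | 60.0% | 65.7% |

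With strong variation and a 10% mean, the result can fall inside 10-35%. At means of 15% or 20% it does not, for these values of s.

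**Step 5: what a 35% six-cycle benchmark would do.** Section 9.1 specifies no such test, so this is illustrative. A one-sided exact binomial test at 0.05 with n = 500 is passed at 194 or more pregnancies (38.8%). For a kit at the plan's ICI rate of 9% per cycle:

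| Cycles completed by every non-pregnant user | Expected rate | Probability of beating 35% |
|---|---|---|
| 6 | 43.2% | 98% |
| 5 | 37.6% | 30% |
| 4 | 31.4% | 0.03% |
| 3 | 24.6% | effectively 0 |

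At n = 384 (pass at 151 or more) the six-cycle entry is 94%. If users were spread evenly over one to six cycles (an assumption), the expected rate would be (9.0 + 17.2 + 24.6 + 31.4 + 37.6 + 43.2)/6 = 27%, well short of 38.8%.

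**The case against.** The case on the other side has four parts.

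*The planned comparison does not use 35%.* Section 9.1 names 10-20%, and section 9.4.1 says the analysis of each hypothesis is the one described in 9.1. This stands. The direct problem in 9.1 is an up-to-6-cycle rate set against what appears to be a one-cycle rate; 10-35% is a risk through section 4.1 only.

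*A reader might infer that ordinary ICI would be declared better than IUI almost every time.* The documents do not support that for a 35% benchmark. The 98% and 94% need every non-pregnant user to complete six cycles. Entry requires only one cycle (5.1), purchase was 2-8 months earlier (section 5), and one kit supplies two inseminations within a cycle (2.3.2). At four cycles the result reverses.

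*A reader might infer that 10-35% is proven too low, or that a six-cycle IUI rate cannot lie below about 45%.* Neither follows. The per-cycle unit in 2.2 is attached grammatically to ICI, and its carry-over to IUI is a reading. The ICI counts come from 53 women using donor semen, with intervals that include 35%. A crude rate over few cycles could also fall in the range: at 10% per cycle, one to four cycles give 10.0%, 19.0%, 27.1% and 34.4%.

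*The ranking of IUI above ICI is less settled than the crossover suggests.* Section 2.2 also cites a review of six trials (708 women) that found too little evidence to say IUI gives more pregnancies or live births, and says of ICI that "over a 6 cycle time frame seems to have comparable rates to its more expensive counterparts". The crossover's 15% is about 14 of 94 cycles. Treating cycles as independent, its 95% interval is about 8-24%, which from unrounded limits is about 41-80% over six cycles.

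What survives is the conflict of units and the clash between the six-cycle reading and the plan's per-cycle rates. Neither depends on the ICI counts or on any test.

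**Conclusion.** The concern holds in limited form. The same 10-35% has a six-cycle label in 4.1, a per-cycle context in 2.2 and no unit at its third appearance. As a six-cycle figure it implies 1.7-6.9% per cycle under a constant rate with six completed cycles, below every per-cycle rate in the plan. That makes it internally inconsistent and probably too low. The six-cycle ICI results of 45% and 46% point the same way but are only suggestive. Which label is correct cannot be decided without the cited source.

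The consequence is conditional: it arises if 10-35% is taken as the six-cycle benchmark for primary hypothesis 1. Its size then depends heavily on how many cycles users complete, which the plan does not state, so no single false-claim probability can be given. The 98% figure is the extreme case only.

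**What to change.** 1. Check 10-35% against its source and give it one stated time unit at both places in section 2.2 and in section 4.1.
2. Do not use it as a six-cycle decision benchmark unless the source confirms that it is one.
3. State in 4.1 and 9.1, in the same words, that the IUI comparison is made per cycle from the survey's cycle-by-cycle answers: pregnancies divided by cycles of use. If the cycle of conception is not recorded, say that a pregnancy is assigned to the last reported cycle. The alternative is a sourced cumulative IUI rate with the same cycle exposure as the respondents.
4. Give the head-to-head rates in 2.2 (IUI 15%, ICI 9%) as a reference, with their uncertainty. Show 62% over six cycles (1 − 0.85^6) only as a constant-rate sensitivity value.
5. Set no minimum for a six-cycle IUI rate from the 45-46% ICI results. If pass probabilities are shown, present 98% (n = 500) and 94% (n = 384) only as the case in which every non-pregnant user completes six cycles.

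The cost is a source check and wording in 2.2, 4.1 and 9.1, with no new data. The benchmark may become less favourable to the kit.
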